#### 9.2 Physical examination

Physical examinations were conducted at each visit. The following systems are also assessed; an 'Other' category was also included:

- General appearance
- Head, eyes, ears, nose, throat
- Skin/dermatologic
- Lymph nodes
- Chest / lungs
- Heart /cardiovascular
- Abdomen
- Extremities

Each was assessed on a 3-point scale:

Job Number: 1555 Customer Reference: Study ID: 020221 SAP Version: 1.0

- Normal or return to normal
- Abnormal not clinically significant
- Abnormal clinically significant

Results and changes from baseline will be summarized per visit, for each treatment group separately.

#### 9.3 Neurological examination

Neurological examinations were conducted at each visit. The following systems were assessed; an 'Other' category was also included:

- Mental status
- Cranial nerves
- Motor
- Reflexes
- Sensory
- Coordination / gait

Each was assessed on a 3-point scale:

- Normal
- Abnormal due to GBM
- Abnormal due to other causes

Results and changes from baseline will be summarized per visit, for each treatment group separately.

#### 9.4 Laboratory tests

Laboratory test results will be summarized for each treatment group separately. Shift tables will be prepared.

#### 9.5 Vital signs

The following will be presented in tables summarizing by-treatment descriptive statistics for the observed and change from baseline values at each visit:

- Pre-injection heart rate
- Systolic blood pressure (BP)
- Diastolic BP
- Respiration

# APPENDIX A: External controls for newly diagnosed GBM

Report 1 from YHEC, attached to PDF

## **APPENDIX B: External controls for recurrent GBM**

Report 2 from YHEC, attached to PDF

## **APPENDIX C: Progression-free survival**

Situation	Date of Progression or Censoring	Outcome
Progression documented between scheduled visits	Actual date of documented progression	Progression
No progression	Date of last radiology assessment demonstrating no progression	Censored
Treatment discontinuation for undocumented progression	Date of last radiology assessment demonstrating no progression	Censored
Treatment discontinuation for toxicity or other reason	Date of last radiology assessment demonstrating no progression	Censored
New anticancer treatment started	Date of last radiology assessment demonstrating no progression	Censored
Progression after more than one missed visit	Date of last radiology assessment demonstrating no progression	Censored
Death before first PD assessment	Date of death	Progression
Death between adequate assessment visits	Date of death	Progression
Death after one or two missed visits (≤ 4 months from last MRI)	Date of death	Progression
Death after more than two missed visits (> 4 months from last MRI)	Date of last radiology assessment demonstrating no progression	Censored
No MRI post baseline and no death within 4 months of baseline and withdrawn from study	Date of withdrawal	Censored

In practice, this is executed as follows:

Take the minimum of the following dates

- Confirmed Progression
- Death
- Withdrawal due to reason "OTHER", "DISEASE PROGRESSION" or "PATIENT ENROLLED IN A TRIAL OF ANOTHER INVESTIGATIONAL AGENT FOR THE TREATMENT OF GBM"

Depending on which of these dates is the minimum decides how PFS is calculated. It is possible that all three of these dates are missing for a patient and therefore they have no minimum date. When two different dates are both the minimum date and it needs to be decided which set of rules to follow then the rules are picked using priority Confirmed Progression > Death > Withdrawal.

e.g. a patient has a confirmed progression and a withdrawal on the same day, both of which occur before death. Use the Confirmed progression rule to derive PFS because Confirmed Progression > Withdrawal.

Minimum Date	Rule to determine PFS date and censoring		
Confirmed Progression	
 
If their last MRI prior to progression was within 4.5 months of their progression, then use confirmed progression date, uncensored
 
Otherwise use previous MRI, censored
 
		
Death	
 
If subject died within 2 months of randomization, use date of death, uncensored
 
If the subject died within 4.5 months of an MRI scan use date of death, uncensored
 
Otherwise use previous MRI, censored
 
		
Withdrawal due to one of the specified reasons	Use last MRI prior to withdrawal, censored		
No minimum date	Use the last MRI, censored		

In the above table there are various conditions which require to use the last MRI as the PFS date. However there are cases when the subject either does not have MRI data or the last MRI was pre baseline. In these cases use the date of study completion, censored.

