#### 1.3 Sample size

#### 1.3.1 Sample size for PFS

The sample size calculations were based on PFS. Table 1 shows the assumptions made.

Table 1: Assumptions Made to Support Sample Size Calculation

Ratio between the treatment arm and the placebo arm	2:1
Accrual period	36 months
Time to accrual of 50% of subjects	22 months
Follow up period	5 months
Loss to follow up, per arm per month	1%
Median PFS for placebo arm	7 months
Test for comparing PFS between arms	Log rank
Type I error	$\alpha$ = 0.01, one sided

To achieve 84% power when median PFS is 11 months in DCVax®-L-treated subjects, 348 subjects would be required in total: 232 in the DCVax®-L arm and 116 in the placebo arm. The corresponding total number of events required is 248.

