#### 3.1.4 Progression-free survival

PFS is defined as the time from randomization until objective demonstration of tumor progression or death, whichever occurs first [10]. If neither tumor progression nor death are known to have occurred by the date of database lock, the date the subject was last known to be alive and progression-free will be used to calculate PFS, which will be considered censored.

When data points, especially in regards to radiographic imaging data, are missing, strong efforts will be made to obtain the missing study information. In spite of these efforts, there may be missing data regarding assignment of primary and secondary endpoints. Detailed rules for the definition of progression-free survival (modified Macdonald criteria) are provided in Appendix C.

Within-Study controls are used for this endpoint.

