#### 11. PATIENT DISCONTINUATION OF ACTIVE TREATMENT

An explanation for discontinuing treatment is recorded for each patient discontinuing treatment on the appropriate CRF/eCRF. The Sponsor, or its designee, must be notified immediately if a patient discontinues treatment. All patients, irrespective of treatment status, will continue to be followed for survival. Treatment in this study must be discontinued for any of the following reasons:

- if the Sponsor decides to stop the study;
- at Investigator's discretion;
- at the patient's request;
- if the patient enrolls in a trial of another investigational agent for the treatment of GBM;
- Grade 4 or life-threatening toxicity (See Section 11, Adverse Events) attributable to DCVax-L:
- injection site reactions of Grade 3 or higher, according to the grading in Appendix E, Modified Grading of Injection Site Reaction Toxicity;
- development of clinical signs and symptoms of autoimmune disease;
- pregnancy;

development of an allergic reaction of Grade 2 or higher, with exception of transient (<1 hour) fever or other constitutional symptoms, localized urticaria, and transient (<30 seconds) shortness of breath, or immunological reaction Grade 3 or higher to DCVax-L, with the exception of low grade fever of <39°C (102.2°F) which resolves spontaneously or with antipyretics within 48 hours.

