## 15.2. DEFINITION OF PROGRESSION AFTER ENROLLMENT

Progression, calculated from the nadir tumor burden (i.e. post operative orBaseline), is defined as one of the following:

- In the case of complete resection during primary therapy: a new measurable tumor at
  the site of the resected tumor, defined as a mass with a longest diameter equal to or
  greater than 1 cm in at least one dimension. If progression is not defined by these
  studies, treatment may proceed and determinations made at the next scheduled MRI.
- In the case of incomplete resection during primary therapy: a 25% increase or greater
  in the residual tumor if the recurrent portion of the tumor is at least 1 cm or greater in
  its longest diameter, measured by MRI and confirmed by scans above as attributable
  to tumor growth;
- If resection is indicated for recurrent disease, while radiographic criteria for progression have not been met: surgical resection, subsequently confirmed as

progressive GBM by Pathology at the clinical site and to be confirmed by independent pathology;

- Appearance of any new lesion/site at least 1 cm in at least one dimension or greater measured by MRI and confirmed by scans above;
- Unequivocal progression of non-measurable disease (either non-enhancing disease seen only on T2/FLAIR images or enhancing disease not meeting size criteria for measurability), such that there is confidence that tumor growth has occurred;
- Death: all deaths are counted as events for the primary endpoint.

Radiographic evidence of disease progression will be evaluated and corroborated by independent radiology review to determine disease progression for purpose of this trial. MRIs to assess disease progression are done every 2 months. Unscheduled MRIs or other testing will be recorded in CRFs/eCRFs. If, during unscheduled procedures, there is evidence of disease progression, it must be confirmed through independent review as described above.

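### The Appendix C PFS algorithm lets an earlier withdrawal, including one for disease progression, displace a later known death, contrary to the plan's own PFS definition; the direction of any bias is not determinable

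*Combined protocol and SAP*

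**What the plan says.** SAP Section 3.1.4 gives the endpoint: "PFS is defined as the time from randomization until objective demonstration of tumor progression or death, whichever occurs first". It provides for censoring only when neither event is known to have happened by database lock. Protocol v7.0 Section 15.2 ends its list of progression criteria with "Death: all deaths are counted as events for the primary endpoint", a line that dates from when PFS was primary.

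SAP Appendix C then has two parts. The situation table counts as events a death before the first assessment, between adequate assessments, or after one or two missed visits (up to 4 months from the last MRI). None of these rows makes an exception for withdrawal. The table also censors treatment stopped for undocumented progression and censors at the start of new anticancer treatment.

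The algorithm that is actually executed begins "Take the minimum of the following dates": confirmed progression, death, and "Withdrawal due to reason 'OTHER', 'DISEASE PROGRESSION' or" entry into another GBM trial. It continues: "Depending on which of these dates is the minimum decides how PFS is calculated". If withdrawal is the minimum: "Use last MRI prior to withdrawal, censored". A patient with no post-baseline MRI is censored at study completion instead. The priority of confirmed progression, then death, then withdrawal applies only to equal dates. The death rule (event if within 4.5 months of an MRI, or within 2 months of randomization) is reached only if death is the minimum date.

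Protocol Section 11 says of patients who stop treatment: "All patients, irrespective of treatment status, will continue to be followed for survival".

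**The concern.** A patient who withdraws because of progression, before independent review has confirmed it, is analysed as progression-free at the last scan. A later death, or a later confirmed progression, is never looked at. Where the reason for withdrawal is progression, the reason for censoring is the outcome itself, so the censoring is informative.

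Within-trial PFS is Secondary Endpoint #3. It is tested in sequence at 2.409% (SAP Section 8.3.1) and stands before within-trial OS. Lost events reduce its power, the PFS curves come out too high, and the reported hazard ratio can shift if the arms differ in how often this happens.

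**Working it through.** **1. One patient under each text.** Illustration on the 2-monthly MRI schedule: last MRI at month 4, withdrawal for 'DISEASE PROGRESSION' at month 5, no confirmed progression, death at month 6.

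- SAP Section 3.1.4: event at month 6, and the condition for censoring is not met.
- Protocol Section 15.2: event.
- Appendix C situation table, death rows: event (2 months from the last MRI, limit 4).
- Appendix C algorithm: the minimum date is month 5, so censored at month 4. The death rule, which 2 months would satisfy (limit 4.5), is not reached.

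The last row of the situation table points the same way as the first three: it censors a withdrawn patient without a post-baseline MRI only if there was no death within 4 months of baseline.

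**2. The plan's own figure.** Inputs from SAP Section 1.3.1: medians 7 and 11 months, one-sided 0.01, power 84%, 2:1 allocation, 248 events. HR = 7/11 = 0.636 and |ln HR| = 0.452.

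Events = (z_α + z_β)² / [(1/3)(2/3)(ln HR)²] = (2.326 + 0.994)² / (0.2222 × 0.2043) = 243, against 248 stated. Power at 248 = Φ(√(248 × 0.2222) × 0.452 − 2.326) = Φ(1.03) = 84.8%, against 84% stated. The figure reproduces.

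**3. Power if events are lost.** The share lost is an assumption; the documents give none.

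| Share lost | Events left | Power, 0.01 | Power, 0.02409 |
|---|---|---|---|
| 0 | 248 | 84.8% | 91.6% |
| 10% | 223 | 80.4% | 88.6% |
| 20% | 198 | 74.9% | 84.7% |
| 30% | 174 | 68.6% | 79.8% |

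**4. Hazard ratio and medians.** If a share q of an arm's events is turned into censoring, that arm's hazard falls to about (1 − q) times its value. Hence rule HR ≈ HR × (1 − q_DCVax-L)/(1 − q_placebo), and each median is divided by (1 − q).

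- Equal q: the ratio cancels and the HR does not move. At 10% the medians become 7/0.9 = 7.8 and 11/0.9 = 12.2 months.
- 10% placebo, 5% DCVax-L: 0.636 × 0.95/0.90 = 0.672.
- 5% placebo, 10% DCVax-L: 0.636 × 0.90/0.95 = 0.603.

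A simulation checks the formula. It used 600,000 patients per scenario, exponential PFS, 2-monthly MRI and an assumed mean of 4 months from withdrawal to death. Each result below is the rule HR, followed by the HR with the withdrawal counted as an event:

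- Equal shares of 10%, 20%, 30%: 0.652 vs 0.652; 0.654 vs 0.657; 0.644 vs 0.648.
- 20% placebo, 10% DCVax-L: 0.721 vs 0.643. Counting only later deaths within 4.5 months gives 0.681.
- 10% placebo, 20% DCVax-L: 0.588 vs 0.662. Counting only later deaths gives 0.622.
- Equal shares with withdrawal tied to patient frailty (assumed gamma variance 0.5 to 1): rule HR lower by 0.006 to 0.04.
- No true effect: 1.00 with equal shares; 1.10 (20/10) or 0.90 (10/20) with unequal shares.

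**5. How many patients could be affected.** Progression confirmed on or before the withdrawal date keeps its event. Crossover requires independently verified progression (Protocol Section 8.4), and SAP Section 1.1 says about 90% of the ITT population crossed over. On that wording about 331 × 0.10 = 33 patients remain, including those who died first or never progressed. As a ceiling that is 33/248 = 13% of the planned events.

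The SAP text on Secondary Endpoint #4 instead says 90% of patients have received DCVax-L. If all 232 randomized to it did so, that leaves 331 × 0.90 − 232 = 66 of 99 placebo patients who crossed over, and says nothing about crossover in the DCVax-L arm. The ceiling therefore depends on which wording is right.

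**The case against.** The strongest defence is that much of the rule is deliberate. PFS requires objective demonstration of progression, corroborated centrally, and the situation table openly censors treatment stopped for undocumented progression. Declining to count an unverified progression is a recognised convention, and that part stands. It does not explain discarding a later death, which needs no radiological confirmation and lies inside the plan's own window. The table gives no precedence between that row and the death rows.

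The consequences are also bounded. The SAP itself expects this endpoint to be confounded by pseudo-progression. It is reached only after earlier gates. SAP Section 5 already tabulates withdrawals by reason and arm. The test is Karrison's weighted log-rank, so the figures above describe the reported hazard ratio and approximate log-rank power, not that exact test. All of this limits severity but does not remove the contradiction. Withdrawal is also undefined: Protocol Section 11 guarantees survival follow-up after stopping treatment, not after leaving the study, so not every later death need be known.

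A reader might infer that the rule favours the arm with the lower hazard. That follows if Table 1's "Loss to follow up, per arm per month" (1%) is read as withdrawal for progression at the same absolute rate in both arms: with ln 2/11 = 0.0630 and ln 2/7 = 0.0990, (0.0630 + 0.01)/(0.0990 + 0.01) = 0.670 would be the true ratio against 0.636 under the rule. The documents do not support this. Loss to follow-up is not withdrawal with a known later death, and nothing states equal absolute rates. If withdrawal follows progression, equal shares are at least as natural, and they leave the ratio unchanged.

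**Conclusion.** The contradiction is certain from the text: the executed algorithm censors patients whom SAP Section 3.1.4, Protocol Section 15.2 and the situation table's death rows would count as events. For withdrawal due to progression, the censoring is informative. The effect is fewer events, PFS overstated in each arm where it occurs, and lower power: 80.4% rather than 84.8% if 10% of 248 events are lost.

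The direction of any hazard-ratio bias cannot be determined, because the documents give no withdrawals by arm. The 0.603 to 0.672 range rests on assumed shares of 5% and 10%, and larger assumed imbalances widen it. The number affected may be small if about 90% did cross over after verified progression. Two further inferences should be avoided: that withdrawal ranks above death (death wins a tie; this is an earliest-date effect), and that these patients are the sickest, which the documents do not say. The point warrants correction but does not bear on the primary endpoint.

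**What to change.** Amend Appendix C before unblinding:

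- Take the minimum of confirmed progression and death first. Count a death inside the stated window as an event despite an earlier withdrawal for 'DISEASE PROGRESSION' or 'OTHER'.
- Keep censoring where new anticancer treatment or another GBM trial came first, as the situation table already states.
- Use the withdrawal rule only when no qualifying event follows.
- Reconcile the 4-month window in the table with the 4.5-month window in the algorithm.
- State whether withdrawal means from treatment or from the study.
- Add one sensitivity analysis that counts withdrawal for 'DISEASE PROGRESSION' as an event at the withdrawal date, read beside the by-arm withdrawal reasons planned in SAP Section 5. It is needed because later deaths recover only part of the shift (0.681 and 0.622 in the unequal cases above).

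The cost is SAP wording and a reordered derivation, with no new data. PFS medians may be slightly shorter.

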## **APPENDIX D: Matching-Adjusted Indirect Comparison**

Matching-adjusted indirect comparison (MAIC) is a technique that is commonly used to help inform cost-effectiveness modelling: an area where treatment effect estimates are frequently required for treatments not compared within the same trial or in trials with a common comparator treatment [32]. MAIC aims to adjust for differences in subject characteristics (both prognostic factors and treatment effect modifiers) between trials, in order to compensate for a lack of randomization, or imbalances between studies. Note that this method relies on the unverifiable assumption that outcomes can be fully predicted from the treatment and that all important prognostic factors and effect modifiers are included in the model [32].

Subject characteristics are identified that are reported in the current phase III study (Study 020221) and in the published data for the control arm. Subjects in the DCVax®-L arm of Study 020221 are then given weights such that overall the weighted averages of their characteristics match those of the control arm of the published study. Characteristics that can be included in some or all of these analyses, depending on what was reported for the control arm in question, are:

- MGMT methylation status
- Performance status
- Surgical status
- Age
- Sex
- Race

More specifically, it is assumed that we have a treatment  $k_1$  that has been studied in population  $s_1$  for which individual patient data (IPD) of covariates  $X_{s1} = \{x_i s_1\}$  are available, and a second population  $s_2$  where the treatment has not been studied, and where only the marginal means of the covariate data  $\overline{X}_{s_2}$  are available. The principle of the method is to translate the observed study results  $Y_{k_1s_1=\{y_i\}}$  in study population  $s_1$  to expected mean study results  $\widehat{Y}_{k_1s_2}$  by weighting the population in study  $s_1$  to make it more similar to population  $s_2$ . This is done using the following steps:

- 1) Re-centre the covariate vectors by subtracting  $\bar{X}_{S_2}$ , thereby generating two new vectors,  $X'_{S1}=X_{S1}-\bar{X}_{S_2}$  and  $\bar{X}'_{S_2}=0$
- 2) Find the values  $\hat{\alpha}$  that minimize  $\sum_{i=1}^{N_{s_1}} \exp(\alpha^T x_{is_1}')$ .
- 3) Apply survival analysis to the reweighted data.

Standard errors will be estimated using a robust sandwich estimator [33].

SAP Version: 1.0

A MAIC will be performed for all the published studies pooled together, and also separately for each

published study.

As a part of evaluating the performance of the weighting, the adjusted sample size will be calculated and reported for each MAIC. This can be calculated as

$$Adjusted \ sample \ size = \frac{(\sum weights)^2}{\sum weights^2}$$

#### **Protocol Synopsis**

Protocol Title: A Phase III clinical trial evaluating DCVax®-L, autologous dendritic cells (DC) pulsed with tumor lysate antigen for the treatment of glioblastoma multiforme (GBM)

Protocol No.: 020221, v7.0

**Study Agent**: DCVax®-L (autologous DC loaded with autologous tumor lysate).

Indication: Treatment of patients with newly diagnosed GBM.

#### Objectives:

Primary: The primary objective of this study is to compare overall survival (OS) between patients randomized to DCVax-L and control patients from comparable, contemporaneous trials who received standard of care therapy only, in patients with newly diagnosed glioblastoma. This endpoint will be assessed using 3 different analyses.

Secondary: The first secondary objective is to compare overall survival (OS) between patients randomized to placebo who received DCVax-L treatment following disease recurrence and control patients from comparable, contemporaneous clinical trials, in patients with recurrent GBM.

#### Study Design:

The study is designed as a randomized, placebo-controlled, double blinded, multi-center, multi-national Phase III clinical trial.

To achieve its primary goals, the trial will randomize approximately 348 patients with newly diagnosed GBM with no evidence of progression at baseline, of which approximately 232 patients will be randomized into the treatment cohort and will receive DCVax-L as adjuvant therapy to standard treatment and approximately 116 patients will be randomized into the placebo cohort and will receive standard treatment supplemented with autologous mononuclear cells (MNC; placebo).

Patients must have a minimum of 5 doses of DCVax-L available to be eligible for randomization. Randomized patients will receive up to 10 immunizations with DCVax-L or placebo over a period of up to 3 years. Some patients in the DCVax-L cohort may not receive 10 immunizations due to insufficient material; in these cases immunizations will be replaced with placebo while maintaining the blind. Patients in either cohort who progress during the study will be offered a crossover (openlabel) option with no unblinding to receive a series of up to 10 immunizations with DCVax-L (depending on DCVax-L availability).

Safety of DCVax-L will be assessed by comparing the frequency and intensity of adverse events, physical and neurological examination, and clinical laboratory testing results during the study period, between DCVax-L treated patients and controls.

Protocol: 020221, v7.0 23SEP2020 Page 2 of 55

Northwest Biotherapeutics, Inc. DCVax®-L, IND #10206

